10.3 Recording Adverse Events

Adverse events (including pre-treatment adverse events) must be recorded on an *Adverse Event Report Form*. The investigator must provide information on the adverse event, preferably with a diagnosis, or at least with signs and symptoms; start and stop dates (and start and stop time if the adverse event lasts less than 24 hours); intensity; causal relationship to IMP; action taken; and outcome. If the adverse event is an overdose, the nature of the

overdose must be stated (for example, medication error, accidental overdose, or intentional overdose). If the intensity changes during the course of the adverse event, this must be recorded on the *AE Intensity Log*.

If the adverse event is *serious*, this must be indicated on the *Adverse Event Report Form*. Furthermore, the investigator must fill out a *Serious Adverse Event Report Form* and report the SAE to Lundbeck immediately after becoming aware of it (section 10.4).

Adverse events, including clinically significant out-of-range clinical safety laboratory values, must be recorded individually, except when considered manifestations of the same medical condition or disease state; in such cases, they must be recorded under a single diagnosis.

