11.1.3 Classification of Adverse Events

Adverse events will be classified according to the time of onset of the adverse event: treatment-emergent adverse event (TEAE) – an adverse event that starts or increases in intensity after the date of Baseline II.

An adverse event is considered causally related to the use of the IMP when the causality assessment by the investigator is *probable* or *possible*.

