11.1.4 Allocation of TEAEs to Treatment Periods

TEAEs will be allocated to treatment periods according to the time of onset of the adverse event:

• *adverse event in the open-label treatment period* – an adverse event that starts or increases in intensity after the date of Baseline II and at or before the date of the last protocol-

LU Study Number: 14861B Trial Site Number: Study Level Pluto ID: CLI 00933680

- specified contact in the study for patients not continuing into the open-label treatment period with memantine, and at or before the date of Baseline III for patients in the APES2.
- adverse event in the open-label treatment period with memantine an adverse event that starts or increases in intensity after the date of Baseline III and at or before the date of the last protocol-specified contact in the study.

Note, the completion Visit in the lead-in studies are the same as the Baseline II Visit in the extension study, and adverse events ongoing or starting at Baseline II and not increasing intensity will only be reported in the lead-in study.

All tables and listings will be presented separately for adverse events in the open label treatment period, and the open label treatment period with memantine.

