18.4.4 Adverse Event Start and Stop Dates

If a stop date is missing due to an adverse event being on-going, the last visit date will be used as the stop date in the classification of TEAEs.

An adverse event with a missing or incomplete start or stop date will be classified as a pretreatment adverse event if the patient was taking placebo in the lead-in study and the following conditions are met:

- The start date is missing or incomplete, and the stop date is prior to the Baseline II visit, or the stop date is incomplete but known to be prior to the Baseline II visit (stop day is missing and stop year and month are before the year and month of the Baseline II visit, or stop day and month are missing and stop year is before the year of Baseline II)
- The start date is incomplete but known to be prior to the Baseline II visit (start day is missing and start year and month are before the year and month of the Baseline II visit, or start day and month are missing and start year is before the year of the Baseline II visit), and no change in intensity

If a start date is missing for an adverse event and the stop date is prior to the Baseline II visit, then the adverse event will be regarded as starting prior to the study and will not be included in the reporting of AEs in the study. In all other instances of an adverse event with a missing start or stop date, the adverse event will be classified as a TEAE.

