- c. Patients who complete the study and do not enter into the open-label treatment period with memantine (sub-study) will have a Safety Follow-up Visit which is at least 4 weeks (+ up to 7 days) after the last dose of IMP. Patients withdrawn will likewise be followed-up 4 weeks (+ up to 7 days) after withdrawal except for those who withdraw their consent. Patients who withdraw their consent should still have a safety follow-up, but the visit must only be recorded in the medical records.
- d. All assessments can be completed over a maximum of two consecutive days, in this case the first day should be considered as the visit day of the study. Note: If a visit takes place over two consecutive days the IMP should be dispensed on the second day, after all assessments have been performed. For visits other than the Baseline II visit, the visit window must allow for the previously dispensed IMP to last for both visit days.
- e. If the date of a patient visit does not conform to the study plan, subsequent visits should be planned to maintain the visit schedule relative to Baseline II. Number of days between 2 visits must not exceed the number of days for which IMP is provided in the wallet cards.
- f. Lead-in study screening visit (Visit 1) data transferred.
- g. Assessments and procedures conducted at Visit 7 (Completion Visit) of the lead-in study will be transferred and will not be repeated at the Baseline II Visit of this extension study.
- h. During evaluation the patient should be compared to Baseline I assessment of the lead-in study.
- i. Data will be transferred from Visit 7 (Completion Visit) of the lead-in study or entered manually to the eCRF if the scale has been administered for the first time at Visit 1 of the extension study.
- j. On-going adverse events and Concomitant Medications at Visit 7 (Completion Visit) from the lead-in study are to be transferred to the eCRF.
- k. Only for adverse events on-going at Completion/Withdrawal Visit and new SAEs.
- 1. As base treatment, donepezil hydrochloride 10 mg/day will be dispensed as wallet cards.
- m. *Patient Identification Card* should only be returned after the last dose of IMP has been taken, that is at the end of the treatment period.

(substudy)]

n. For patients who may be eligible to participate in the open-label treatment period with memantine (substudy), it is suggested that the *Informed Consent Form* is provided.

LU Study Number: 14861B Pluto ID: CLI_00933680

Status: Final

Page 41 of 48

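### SAP 18.4.4 tests for any change in intensity where 11.1.3 and 11.1.4 require an increase after Baseline II, so an eased adverse event with a partial start date can be counted as a TEAE

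*SAP*

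**What the plan says.** SAP 11.1.3 defines a TEAE as "an adverse event that starts or increases in intensity after the date of Baseline II". SAP 11.1.4 allocates events to periods on the same basis and adds that "adverse events ongoing or starting at Baseline II and not increasing intensity will only be reported in the lead-in study".

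SAP 18.4.4 deals with missing and incomplete dates. Its opening rule covers both kinds and classes an event as a "pretreatment adverse event if the patient was taking placebo in the lead-in study and the following conditions are met". Two bullets follow:

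- The first concerns events that had already stopped: "The start date is missing or incomplete, and the stop date is prior to the Baseline II visit", or a partial stop date known to be earlier. It has no intensity condition.
- The second concerns events whose partial start date is known to be earlier than Baseline II. It ends "start year is before the year of the Baseline II visit), and no change in intensity".

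The section closes: "In all other instances of an adverse event with a missing start or stop date, the adverse event will be classified as a TEAE".

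Two further provisions determine what the derivation will see. Protocol 10.3 states "If the intensity changes during the course of the adverse event, this must be recorded on the" AE Intensity Log, without regard to direction. Footnote j to the first flow chart in SAP Appendix II states "On-going adverse events and Concomitant Medications at Visit 7 (Completion Visit) from the lead-in study are to be transferred to the eCRF".

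**The concern.** The definition and the date rule apply different tests to an event that was already present at Baseline II. The definition asks whether it got worse after Baseline II. The date rule asks whether its intensity changed, with no direction and no time reference. An event that improved passes the first test and fails the second.

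A missing day or month could then decide whether a resolving lead-in event is reported as emerging in the extension. The primary objective is long-term safety and tolerability, and adverse events are the first safety endpoint listed in SAP section 3. An event misclassified in this way would appear in the extension's TEAE tables although 11.1.4 assigns it to the lead-in study alone.

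**Working it through.** The point is about wording, so the check is to follow one event through both sets of rules.

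**The event.** A lead-in placebo patient has an adverse event whose start month is known and earlier than the month of Baseline II, with the day missing. The event is still present at Baseline II. The first bullet of 18.4.4 does not apply, because the event did not stop before Baseline II; if it is still ongoing at the end, 18.4.4 sets its stop date to the last visit. The text does not say whether the bullets are joined by *and* or *or*. They are taken here as alternatives, which is the reading more favourable to the plan.

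| Course of the event | Complete start date (11.1.3, 11.1.4) | Partial start date, catch-all read to cover incomplete dates (18.4.4) | Partial start date, catch-all read strictly (18.4.4) |
|---|---|---|---|
| Unchanged | Lead-in only | Pretreatment | Pretreatment |
| Eased after Baseline II | Lead-in only | **TEAE** | Not classified |
| Changed only before Baseline II, with that history in the data | Lead-in only | **TEAE** | Not classified |
| Increased after Baseline II | TEAE | TEAE | Not classified |

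The rules disagree in the second and third rows. The disagreement comes only from the completeness of the date, since in every row the start is known to precede Baseline II. The protocol's own TEAE definition (16.9.1) uses the start date alone, so it would not make the eased event a TEAE either.

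**Which reading of the catch-all.** The opening sentence of 18.4.4 covers missing or incomplete dates; the catch-all says only *missing*. On the strict reading even a worsened event with a partial start date is left unclassified by 18.4.4, so the bullet's intensity condition would send no event anywhere. The wider reading is therefore the natural one, but it remains a reading.

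**How many patients could be concerned.** The plan's sample-size figure reproduces: (3 × 310 + 3 × 280) × 0.85 × 0.85 = 1770 × 0.7225 = 1278.8, stated as about 1280. Each lead-in study has three arms, one of them placebo (protocol Appendix IV). So:

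- lead-in placebo patients: 310 + 280 = 590
- lead-in placebo completers at the planned 85%: 590 × 0.85 = 501.5
- of these, eligible and completing the extension at the second 85%: 501.5 × 0.85 = 426.3

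Placebo patients entering the extension therefore lie between about 426 and about 501 on the plan's own assumptions, and about 500 is an upper bound. The number of affected events would be this count multiplied by the proportion with an event present at Baseline II, the proportion of those with a partial start date known to be earlier, and the proportion of those with a recorded change that is not an increase after Baseline II. The documents give none of these three proportions, so no event count is offered.

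**The case against.** The strongest reply is that 11.1.3 and 11.1.4 are the governing definitions and 18.4.4 only handles dates. Read with them, *change* is shorthand for the one change that the SAP cares about. On the strict reading of the catch-all, the event falls back to 11.1.3 and is classified correctly. The sponsor may well have meant *increase*, but the text does not say so. The SAP uses both words: 11.1.1 speaks of events that change in intensity without giving a direction, and protocol 10.3 has every change logged. A programmer who follows 18.4.4 as written would flag the eased event.

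Over-counting TEAEs can also be defended as caution in a safety study. That holds when timing is unknown. Here the bullet applies only when the start is known to precede Baseline II, and improvement is not evidence of emergence.

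Several limits on the size do stand:

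- A mild event cannot ease to a lower grade, so only events that were moderate or severe can fail the condition by easing.
- Exclusion criterion 7 removes patients whose moderate or severe ongoing event the investigator considers a potential safety risk.
- Adverse-event tables mainly count patients, so a patient who has another TEAE adds nothing to overall incidence.
- Footnote j says that ongoing events are transferred. It does not say that their lead-in intensity history comes with them, so the third row of the table is conditional.

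A reader might go further and infer that the bullet's intensity test affects all lead-in arms. The documents do not support that: the bullet is limited to lead-in placebo patients. Idalopirdine patients have no pretreatment route through these bullets at all, which is a different problem.

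**Conclusion.** The inconsistency stands. Under the second bullet of 18.4.4, an eased event with a partial but known pre-Baseline II start loses pretreatment status. It becomes a TEAE if the catch-all covers incomplete dates, and is left unclassified by 18.4.4 if it does not. The same event with a complete date is not a TEAE. An event whose intensity changed only before Baseline II is treated in the same way, provided that the history is in the extension data.

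The direction is over-counting of TEAEs. The number is probably small and not derivable from the documents; its source is at most about 500 lead-in placebo completers, given the planned 85% completion rate. A reader might infer that overall TEAE incidence is materially inflated, or that a particular event count can be stated. Neither is supported. This is a low-priority wording correction, worth making because it bears on the primary safety objective.

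**What to change.** In the second bullet of SAP 18.4.4, replace *and no change in intensity* with *and no increase in intensity after the date of Baseline II*. In the closing sentence, extend *missing* to *missing or incomplete*. The eased event and the event that changed only before Baseline II then become pretreatment, in line with 11.1.3 and 11.1.4. An event that worsens after Baseline II is a TEAE under either date pattern, so no worsening is hidden.

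The cost is two phrases in the SAP and the matching conditions in the adverse-event derivation, with no new data.

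A reader might take this to bring all of 18.4.4 into line with the definitions. It does not. Because the pretreatment route is limited to lead-in placebo patients, an unchanged event with a partial pre-Baseline II start in a lead-in idalopirdine patient, not known to have stopped before Baseline II, would still fall to the catch-all, against the note in 11.1.4. The SAP should reconcile that restriction separately, preferably in the same revision, because widening the catch-all makes its effect explicit.

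### The missing-date default in SAP 18.4.4 can label an adverse event with a known onset on or before Baseline II as treatment-emergent, in conflict with SAP 11.1.3 and 11.1.4

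*SAP*

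**What the plan says.** SAP 11.1.3 defines a TEAE as "an adverse event that starts or increases in intensity after the date of Baseline II". SAP 11.1.4 then assigns TEAEs to the two open-label periods by onset or worsening after Baseline II or Baseline III. It notes that "adverse events ongoing or starting at Baseline II and not increasing" in intensity are reported in the lead-in study only, and it has all adverse event tables and listings made separately by period.

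SAP 18.4.4 deals with missing dates in four steps:

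1. Ongoing events: where no stop date exists because the event has not ended, the date of the last visit stands in for it when TEAEs are classified.
2. A pre-treatment route. An event whose date is missing or incomplete "will be classified as a pretreatment adverse event if the patient was taking placebo in the lead-in study and the following conditions are met". One condition begins "The start date is missing or incomplete, and the stop date is prior to the Baseline II visit"; the other begins "The start date is incomplete but known to be prior to the Baseline II visit" and also requires unchanged intensity.
3. An exclusion route: "If a start date is missing for an adverse event and the stop date is prior to the Baseline II visit", the event is taken to precede the study and is left out.
4. The default: "In all other instances of an adverse event with a missing start or stop date, the adverse event will be classified as a TEAE".

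SAP 17, which lists changes from the protocol's analyses, mentions only the C-SSRS summary. No section states which of 11.1.3, 11.1.4 and 18.4.4 governs if they disagree.

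**The concern.** Whether an event is treatment-emergent depends on when it began or worsened. If the start date is complete, the stop date adds nothing to that decision. The default in 18.4.4 nevertheless responds to a missing stop date alone, without asking whether the start date is already known.

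The records it could reach are foreseeable. Footnote j to protocol Panel 2 has adverse events ongoing at lead-in Visit 7 transferred to the extension eCRF, so events with a lead-in onset will be in the database. TEAE summaries answer the study's primary objective, long-term safety and tolerability. A rule that gives a different class from the SAP's own definition leaves two competent programmers free to produce different tables.

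**Working it through.** The plan states no figure on this point, so the check is a reading of the rules in order.

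**Step 1: what each exit from TEAE status in 18.4.4 requires of the start date.**

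- Pre-treatment, first condition: missing or incomplete.
- Pre-treatment, second condition: incomplete, but known to be before Baseline II.
- Exclusion: missing.

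A complete start date meets none of these.

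**Step 2: apply the rules to events with onset known to be before Baseline II and no rise in intensity.** Under 11.1.3 and 11.1.4 none of these is a TEAE.

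| Start date | Stop date | Former placebo, by 18.4.4 | Former idalopirdine, by 18.4.4 |
|---|---|---|---|
| Complete | Complete, after Baseline II | Not a TEAE (11.1.3 applies) | Not a TEAE (11.1.3 applies) |
| Complete | Missing because ongoing (last visit date used) | Not a TEAE | Not a TEAE |
| Complete | Missing for another reason | **TEAE by default** | **TEAE by default** |
| Partial, known to be earlier | Any of the three | Pre-treatment | TEAE by default, if *missing* is read to include *incomplete* |

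A complete start date that falls on Baseline II itself gives the same results in the first three rows, because 11.1.3 requires onset after that date.

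**Step 3: compare rows.** The first three rows differ only in the stop date, yet the class changes. In a former placebo patient with an unexplained missing stop date, a partial early start date gives pre-treatment while a complete one gives TEAE. Better evidence of early onset leads to the wrong class. Caution about unknown onset cannot explain this, because onset is known.

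**Step 4: follow the event into the tables.** By 18.4.4 the event is a TEAE. By 11.1.4 it belongs to the open-label period only if it began or worsened after Baseline II, and to the memantine period only if it did so after Baseline III. It did neither. There are two possible outcomes:

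- The program treats the 18.4.4 flag as sufficient. The event enters the open-label TEAE summaries and is also in the lead-in report.
- The program applies the 11.1.4 allocation. The event is a TEAE that belongs to no period.

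**Step 5: the placebo condition.** The complete-start case arises in both arms, so removing the placebo-only condition would not cure it. That condition does produce the related misclassification in the last row for former idalopirdine patients, so the two need to be corrected together.

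**The case against.** The strongest reply is that the default should not be read alone. The note in 11.1.4 deals expressly with events carried over from the lead-in study and gives the right answer, and tables are built by period from onset. This stands in part. A reader might infer from 18.4.4 that known lead-in events will enter the primary safety tables, and the documents do not establish that. They do not rule it out either, since no order of precedence is given, and the second outcome in Step 4 is also a defect.

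The second reply is that such records should be rare, and this stands. Unresolved transferred events would normally count as ongoing and receive the last visit date. Protocol 8.5 has non-serious events still present at safety follow-up recorded as ongoing, protocol 10.3 requires start and stop dates, and protocol 11.1.1 provides for entry checks and monitor review. Routes to an unexplained missing stop date remain, such as loss to follow-up (protocol 5.4), or withdrawal of consent, after which follow-up is kept only in the medical records (protocol 8.5). A programmer might treat some of these as ongoing, but the SAP does not say so.

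A reader might also infer that the serious-event and withdrawal tables are materially inflated. Nothing in the documents shows this. Serious events are followed until the outcome is known, and exclusion criterion 7 in protocol 5.3 keeps out patients with a moderate or severe ongoing lead-in event judged a potential safety risk.

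Finally, any error adds events to descriptive tables and hides no signal. That limits the harm but does not make the class correct.

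**Conclusion.** The default is wrong as written. On its literal reading it classifies by a missing stop date when a complete start date already settles the matter, in both lead-in arms. That contradicts 11.1.3 and 11.1.4 and is not declared as a change. Whether the event reaches the open-label tables or is left without a period depends on which section the program follows.

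The effect is limited. The class is confined to stop dates missing for a reason other than being ongoing, and the direction is over-reporting. No count can be given. It is tempting to multiply the expected lead-in completers, 1770 × 85% ≈ 1504, by assumed rates of carried-over events and of missing stop dates. The documents contain neither rate, and 1504 counts completers, not patients who roll over. The conclusion does not depend on a count. It rests on a literal reading of 18.4.4 and on the absence of any statement of precedence.

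**What to change.** Replace the default sentence in SAP 18.4.4 with text to this effect:

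> An adverse event whose start date is complete, or is partial but shows onset on or before Baseline II, is classified under 11.1.3 and 11.1.4, whatever its stop date and lead-in treatment. If onset was on or before Baseline II, it is a TEAE only if intensity increased after Baseline II. Only an event whose available start and stop information cannot show onset on or before Baseline II is a TEAE by default.

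Also state that 11.1.3 and 11.1.4 prevail over 18.4.4, and align the placebo-only condition on the pre-treatment route with the same rule, so that a partial early start date is handled alike in both lead-in arms.

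The cost is one SAP sentence, with the consequential alignment in the same section, and one programming condition. No data collection changes, and events of unknown onset still default to TEAE, so no caution is lost.
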